1.0 Objectives

1.1 Study Objectives

The long term goal of this project is to determine the likely health effects of very low nicotine content in cigarettes, in conjunction with availability of nicotine-containing electronic cigarettes (e-cigs) among smokers with mental health conditions (SMHC). This will be tested in a rigorous randomized controlled trial design. We plan to use a comprehensive set of measures of proven validity and reproducibility, including toxicant exposure, addiction and mental health to assess these effects. The specific objective of this study is to recruit a cohort of 240 current exclusive daily SMHC (diagnosed using the MINI International Neuropsychiatric Interview) and to measure a comprehensive battery of behavioral and health indicators at 4 and 8, 12 and 16 weeks after being randomized to use either normal nicotine content (NNC) Spectrum cigarettes (11.6 mg nicotine/cigarette) or very low nicotine content (VLNC) Spectrum cigarettes (0.2 mg nicotine/cigarette) while also having access to a JUUL e-cig (JUUL Labs, Inc.) containing either 0% or 5% nicotine strength e-liquids in a randomized double-blind, placebo-controlled 2 by 2 design. Our central hypothesis is that key markers of harms to health (e.g. urinary NNAL, exhaled CO, measures of addiction, and mental distress) will be significantly improved among SMHC who are provided very low nicotine cigarettes and high nicotine e-cigs. Study aims are:

Aim 1: To determine whether SMHC have lower levels of markers of harm (e.g. urine NNAL, exhaled CO, measures of mental health) and cigarette addiction when switched to VLNC cigarettes, as compared with NNC cigarettes, at the end of the randomized phase (week 16).

Aim 2: To determine whether SMHC have lower levels of markers of harm (urine NNAL, exhaled CO) and cigarette addiction when provided with nicotine-containing versus zero nicotine electronic cigarettes, at the end of the randomized phase (week 16).

Aim 3: To determine whether use of VLNC cigarettes increases the proportion of smokers who completely switch away from combustible tobacco use (no cigarette use in the past 7 days and CO < 6ppm), as assessed (a) at the end of the randomized phase (week 16) and (b) 4 weeks after the end of the randomized phase of the trial (week 20), compared to those using NNC cigarettes.

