1.3 Secondary Study Endpoints

Secondary endpoints include exhaled CO, Kessler-6 score, and cigarette/e-cigarette dependence using Penn State Cigarette Dependence Index (PSCDI) and Penn State Electronic Cigarette Dependence Index (PSECDI), at week 16, and cigarette abstinence (no cigarette use in the past 7 days and CO < 6ppm) at week 20.

Additional endpoints include:

Health effects and toxicant exposure measures: Pulmonary Function Tests (PFT), Clinical COPD Questionnaire (CCQ), urinary CYMA (biomarker for acrylonitrile [volatile organic compound] exposure), 3HPMA (biomarker for acrolein [volatile organic compound] exposure, cotinine (biomarker of nicotine exposure)

Mental health measures: Center for Epidemiological Studies-Depression (CES-D), Overall Anxiety Severity and Impairment Scale (OASIS), Quick Inventory or Depressive Symptomatology (QIDS), Perceived Stress Scale (PSS)

Nicotine/Tobacco use and addiction measures: daily cigarette use, daily e-cig use, Fagerstrom Test for Nicotine Dependence (FTND), Hooked on Nicotine Checklist (HONC), , Minnesota Nicotine Withdrawal Scale (MNWS)

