3.3 Early Withdrawal of Subjects

3.3.1 Criteria for removal from study

The PI reserves the right to remove a participant from the study for any reason, based on their discretion.

Criteria for withdrawal prior to randomization

- **Participant reports using non-cigarette nicotine products at Visit 2 AND Visit 3.**
Includes cigars, pipes, snuff, chew, hookah, electronic cigarette, marijuana, IQOS, or any other illegal smoked substance, or any other nicotine containing product.
- **Participant's total cigarette consumption includes more than 10% of non-research cigarettes at Visit 3**
- **Participant has reduced their cigarette consumption by more than 50% compared to baseline (Visit 1) cigarettes per day (CPD) at Visit 2 or Visit 3.** This does not include situations of illness or other circumstances that would interfere with the participants' normal smoking behavior.
- **Participant must have smoked a total of 25 or more cigarettes in the past 6 days at Visit 2 and Visit 3.** This does not include situations of illness or other circumstances that would interfere with the participants' normal smoking behavior.
- **Reporting a quit attempt**

These circumstances of withdrawal may be taken on a case-by-case basis and actual withdrawal of the participant will be decided by the researcher. For example, continuation in the study may be possible if the participant has acted in good faith during the study.

Criteria for general withdrawal

Participants may be discontinued by the PI at any point during the study for the following reasons:

- **Missing their randomization visit:** If a participant misses Visit 3, the participant will be considered for withdrawal from the study.
- **New pregnancy:** Participants who report a new pregnancy at any point during the study will be withdrawn. (Except Visit 7; Note: no study products will be provided to the participant at Visit 7)
- **Suicide attempt:** If at any time during the study it is discovered that a participant has made a suicide attempt, they will be withdrawn from the study.
- **Cardiovascular disease (CVD) event requiring inpatient hospitalization:** CVD typically includes MI (heart attack), PTCA (angioplasty/stenting), bypass surgery, stroke, peripheral vascular disease (arterial blockages in arms or legs leading to procedure or surgery). Less common CVD problems would be new cardiac arrhythmias (e.g., new atrial fibrillation) or new valvular disease (e.g., mitral or aortic regurgitation).

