- **DVT/PE (deep vein thrombosis/pulmonary embolism, i.e., blood clots in the venous system) requiring inpatient hospitalization.**
- **Elevated blood pressure at any visit (systolic >159 mmHg or diastolic >99 mmHg).**
- **Adverse events related to e-cig use:** Adverse events will be monitored at every study visit.
- **Significant smoking rate increase compared to baseline:** A participant will be withdrawn from the study if they meet BOTH of the following criteria (any visit prior to Visit 7):
 - The average cigarette per day (CPD) increase by more than 100% from the average CPD at Visit 1
 - The average of two consecutive expired breath carbon monoxide measurements increase according to the following:
 - CO is greater than 50 ppm if CO at Visit 1 is <20 ppm.
 - CO is greater than 60 ppm if CO at Visit 1 is 20 – 34 ppm.
 - CO is greater than 70 ppm if CO at Visit 1 is 35 – 49 ppm.
 - CO is greater than 80 ppm if CO at Visit 1 is 50 – 60 ppm.

- CO is greater than 90 ppm if CO at Visit 1 is 61 – 70 ppm.
- CO is greater than 100 ppm if CO at Visit 1 is 71-80 ppm.
- CO is greater than 110 ppm if CO at Visit 1 is 81-90 ppm.
- CO is greater than 120 ppm if CO at Visit 1 is 91-100 ppm.

- **Worsening substance abuse** in which the participant is behaving inappropriately at visits or demonstrates an inability to continue with the study.
- **Any inpatient hospitalization or debilitation** in which participation in the study could be detrimental to the recovery process. This will be self-reported by the participant and will be reviewed by the site PI and medical professional to determine whether continued participation in the study is appropriate (this could include recovery from a major surgery, worsening of psychiatric symptoms, etc.).
- **Use of recreational (illegal) THC products that are vaped.**
- **Participant choice:** Participants may choose to remove themselves from the study by informing the research team verbally or in writing at any point during the study.
- **Participant behavior:** If a participant is behaving in an inappropriate or threatening manner, admits to lying about eligibility criteria, is participating in other smoking research studies that could affect the primary outcome measures, appears/admits to giving away/selling study products, consistently loses study products etc., then the PI can withdraw him/her from the study at the PI's discretion.

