Procedure for suicide risk at all visits where QIDS questionnaire is administered: If participants indicate an answer of > 0 on item 12 of the QIDS questionnaire, the MINI Suicide module will be administered. Scores of ≥ 9 on the MINI Suicide module will require an assessment with a licensed clinician to document a clinical plan and a determination of retention or termination from the study.

Procedures during COVID-19:

Visit 2 will be completed in-person. Participants will be screened for COVID-related symptoms using a modified version of the Patient Screening Questions from the Penn State Health website. The written informed consent process will take place in person using the paper Consent Form HRP-580 uploaded in the "Consent Forms and Recruitment Materials" section of the IRB application. During this process, the usual discussion of procedure, risks, side effects, confidentiality, voluntary participation, and right to refuse participation without prejudice will be explained to the participant. Participants must be capable of understanding the nature of this study, its potential risks, discomforts and benefits before signing consent. Participants will receive a signed copy of the form.

Participants will be asked to provide photo ID to verify the age given in Screener 2. They will have to complete the final eligibility requirements at this visit in accordance with the inclusion/exclusion criteria mentioned above:

1. Obtain urine sample for pregnancy determination for women of child-bearing potential (those who have had a period in the past 12 months) and who have not had a hysterectomy
2. Measure exhaled CO
3. Measure vital signs (blood pressure and heart rate)

Participants will be asked for their cigarette log from the prior week. Additional biomeasures will be obtained (e.g., pulmonary function tests, weight, height) as outlined in Revised Table 1.

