8.3 Statistical methods

Basic baseline statistics including means (standard deviations) and frequency distributions (percentages) will be reported for demographic characteristics, smoking characteristics, nicotine dependence, and nicotine and toxicant exposure. Characteristics will be reported by the four treatment arms to identify treatment arm imbalances. Numerical baseline characteristics will be compared among four arms using ANOVA tests or nonparametric Kruskal-Wallis tests when appropriate. Categorical variables will be compared using chi-square tests or Fisher's exact tests. The focus of the statistical analysis will be the difference between four trial arms in terms of the biomarkers of toxicity and health effects. Analyses will be conducted in two approaches, which will address our research questions in two different angles. The first approach is a simplified and streamlined one, the longitudinal measurements of these biomarkers over the 16-week period will be summarized by using just the baseline (visit 3, pre-randomization) and final (visit 7, end of randomization period) measurements. Analysis of Covariance (ANCOVA) models will be used to compare the final measurements among the four arms, while the baseline measurements will be treated as controlled covariates in the model. Specifically, the comparisons between arms 1 and 3 and between arms 2 and 4 answer whether switching to very low nicotine cigarettes leads to lower markers of harm as compared to continuing on normal nicotine cigarettes. This addresses specific Aim 1. Furthermore, we will study if this reduction is the same when combined with 5% nicotine e-cigs (arms 1 and 3) and combined with placebo e-cigs (arms 2 and 4). Similarly, comparison between arm 1 and arm 2 reveals if access to nicotine versus placebo e-cigs impacts these biomarkers. This will address Aim 2. In particular, we will test if the arm 3 has the best outcome as stipulated in Aim 2. These analyses will be conducted using ANCOVA models with interaction terms between traditional cigarettes (normal nicotine vs. very low nicotine) and e-cig (5% vs. 0%). Appropriate transformation may be done on some of the outcome variables (for example log-transformation) to make sure the underlying statistical assumptions are all satisfied. Note that for NNAL, one of our main biomarkers of toxicity; it can only be analyzed using the first approach due to the limitation of number of measures.

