The second approach for biomarker analysis will use the longitudinal data analysis to model all the repeated measurements of these biomarkers over the entire 16 weeks. Their trajectories will be plotted for each of the 4 arms. Linear mixed-effect models will be used to model the biomarker measurements on the following predictors: time after randomization (X1, which can be measured in weeks (continuous or visit number (categorical))), normal vs. low nicotine cigarettes (X2), 5% nicotine e-cig vs. placebo e-cig (X3), the interaction between cigarette and e-cig (X2*X3), and the interaction between X1 and X2, X3, X2*X3. In particular, the three-way interaction of X1, X2 and X3 indicates an interaction between cigarette type (NNC versus VLNC) and e-cig type (nicotine versus placebo) on their effect on the change of these markers of harms to health over time. Note that the time variable (X1) can be treated as either categorical or continuous, which will lead to different statistical models – growth curve model vs repeated-measure ANOVA models. If X1 is treated as categorical, then the estimated means and 95% confidence interval (CI) values of the outcome variables will be reported using tables. If X1 is treated as continuous, then the point estimates and 95% CI of the coefficients (rate of changes) will be reported. The baseline (before randomization) measures of the outcome variables will be included in the model as a controlled covariate. Family-wise type-I error rate due to multiple comparisons will be controlled at the visit level (if X1 is treated as categorical) using Bonferroni method. Again, appropriate transformation of the outcome variable may be carried out – similar to the first approach.

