Intent-to-treat (ITT) principle will be adopted for the analyses in both approaches. Additionally, the measurements of tobacco use and addiction and measurements of mental health will be monitored and summarized, and will be compared across these arms in a similar statistical fashion as described above. Self-reported compliance will be reported for all participants. For participants in arm 4 (VLNC plus placebo ecigs) their compliances will be further evaluated using biomarkers. Comparison on the outcome variables will be made between compliers vs non-compliers within arm 4 participants only. All analyses will be conducted using statistical software SAS version 9.4 or higher (SAS Institute, Cary, NC, USA) and R Programming language version 3.6.1 or higher (R Foundations). All tests will be two-sided and the statistical significance level to be used is 0.05.

Adjusted models will evaluate the treatment effect while adjusting for covariates, such as gender, age, race, SDOH scoring, and other baseline factors.

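### Week-16 Kessler-6 comparison does not account for withdrawals that depend on mental health, so a harm of VLNC cigarettes could be understated

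*Combined protocol and SAP*

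**What the plan says.** Mental health is part of the main question. Aim 1 (section 1.1) compares "markers of harm (e.g. urine NNAL, exhaled CO, measures of mental health) and cigarette addiction when switched to VLNC cigarettes" with those on NNC cigarettes at week 16, and section 1.3 states "Secondary endpoints include exhaled CO, Kessler-6 score" among the outcomes at that visit.

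Section 8.3 states that "measurements of mental health will be monitored and summarized, and will be compared across these arms in a similar statistical fashion as described above". Two approaches are described there. In the first, outcomes are "summarized by using just the baseline (visit 3, pre-randomization) and final (visit 7, end of randomization period) measurements", and arms are compared by ANCOVA. The second is to "use the longitudinal data analysis to model all the repeated measurements of these biomarkers over the entire 16 weeks" in a linear mixed model. Intention to treat is named for both. No missing-data method, rule for psychiatric withdrawals or sensitivity analysis is given.

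Three withdrawal routes depend on mental health:
- Section 3.3.1: if it is discovered that "a participant has made a suicide attempt, they will be withdrawn from the study".
- Section 3.3.1: withdrawal after inpatient hospitalisation or debilitation, decided on review by the site investigator and a medical professional, where "this could include recovery from a major surgery, worsening of psychiatric symptoms, etc".
- Section 7.2: a MINI suicide score of 9 or more leads to a clinician assessment and "a determination of retention or termination from the study".

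Section 3.3.2 asks anyone withdrawn at a visit to complete that visit. It then describes week-16 contact for participants who withdraw themselves and for those lost to follow-up. It is silent on those withdrawn by the investigator. Sections 9.2 and 9.7 send adverse events and mental-health changes to the monitoring committee with descriptive statistics.

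**The concern.** Whether a week-16 Kessler-6 score exists can depend on the thing it measures. A participant who deteriorates badly enough to be withdrawn by the investigator has no described route to a week-16 assessment, and the ANCOVA then averages over those who remained. If deterioration is equally common on both cigarette types, this does little to the difference between them. If switching straight to VLNC cigarettes destabilises some participants, more of the high scores go missing from the VLNC arms and the difference moves toward zero.

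The protocol presents the trial as evidence for a regulator on whether a low-nicotine standard is feasible in a vulnerable group. A null Kessler-6 result would be read as reassurance, and the plan should not let differential removal contribute to it.

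**Working it through.** **The plan's own figure.** There is none for Kessler-6. The sizing in section 8.2 concerns NNAL and abstinence, and the documents state no Kessler-6 standard deviation, dropout rate or rate of psychiatric withdrawal. From the documents come only the group sizes (60 per arm, so VLNC v NNC is 120 v 120) and the two-sided 5% level. Everything else below is an assumption.

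**Effect on the ANCOVA.** Let a proportion p1 (VLNC) and p0 (NNC) deteriorate by J points, and let a fraction w of those have no week-16 score. Assume deterioration is unrelated to baseline and nothing else is missing. Then:

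- True difference = J × (p1 − p0)
- Expected observed difference = J × [p1(1 − w)/(1 − p1·w) − p0(1 − w)/(1 − p0·w)]

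With J = 8, p1 = 0.10 and p0 = 0.02, the true difference is 8 × 0.08 = 0.64 points.

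| w | Calculation | Observed difference |
|---|---|---|
| 20% | 8 × (0.08/0.98 − 0.016/0.996) | 0.52 |
| 50% | 8 × (0.05/0.95 − 0.01/0.99) | 0.34 |
| 80% | 8 × (0.02/0.92 − 0.004/0.984) | 0.14 |

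If p1 = p0 the expression is zero, so the bias needs a difference in rates between cigarette types.

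**A second set of assumptions.** A simulation with a 10-point worsening, Kessler-6 bounded at 0–24, mean 6, SD 5 and baseline correlation 0.6 gives the same direction. With 10% v 3% worsening, the true 0.67–0.68 is estimated as 0.52, 0.36 and 0.00 when 25%, 50% and 100% are missing. With 5% v 1%, the true 0.38–0.40 becomes 0.29, 0.20 and 0.01.

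**Chance of a significant harmful result** (8 points, 10% v 2%, SD 5, correlation 0.6): 19% with everyone scored, 4% when 80% of those who deteriorate are missing.

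**Mixed model.** Simulating scores at weeks 4, 8, 12 and 16 under the same inputs with 80% withdrawn gives two cases:
- Event between visits, no later score taken: estimate 0.11 against a true 0.62, no better than the ANCOVA.
- Score taken at the withdrawal visit: estimate 0.41 against a true 0.65, so 0.24/0.65, or about 37%, is still lost.

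**Comparing the events themselves** (Fisher's exact test, 120 v 120): power is 68% for 10% v 2% if every deterioration is counted. If only the withdrawn 80% are counted (0.8 × 10% = 8% v 0.8 × 2% = 1.6%) it is about 54%. For 5% v 1% it is about 28%.

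**The case against.** A reader might infer that the protocol automatically removes everyone who worsens psychiatrically, so that the worst outcomes have no week-16 score by rule. The documents do not support that. The list in section 3.3.1 opens with wording that leaves discontinuation to the investigator. Of these routes only the suicide-attempt item is worded as definite; psychiatric worsening and a high MINI score lead to a reviewed decision that may be to retain. Silence in 3.3.2 about investigator-withdrawn participants is not a ban on contacting them.

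A reader might also infer that most of a harm would vanish. That takes a high missing fraction: 0.14 of 0.64 is about 78% lost at 80% missing, but at 20% missing the loss is about 18% (0.12 of 0.64). Section 3.2 excludes uncontrolled mental illness and recent inpatient treatment, and the team's earlier trial of gradual reduction reported no significant change in depression or anxiety scores, so such events may be few.

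Nor are the data simply discarded. Participants withdrawn at a visit are asked to complete it, the COVID-period schedule has Kessler-6 at weeks 4, 8, 12 and 16, and the mixed model uses those scores. Psychiatric events also reach the monitoring committee.

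Finally, missingness is not the main reason such a harm would be missed: with complete scores, power is only 19% in the illustration.

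These points limit the size. They do not close the gap. A suicide attempt or admission can fall between visits, naming intention to treat does not supply a score that was never collected, and descriptive safety tables are not part of the planned arm comparison.

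**Conclusion.** The gap is real but narrower than the two readings above. Some withdrawals depend on mental health, week-16 contact is not described for participants the investigator withdraws, and section 8.3 has no analysis that accounts for them. If such withdrawals are more frequent on VLNC cigarettes, the Kessler-6 difference is biased toward no harm. If they are rare or balanced between cigarette types, the bias is small.

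The amount cannot be fixed from the documents. In the illustration, the loss from a true 0.64 points runs from about 0.12 to 0.50 as the missing fraction goes from 20% to 80%. The mixed model recovers part of that only if a score is taken at the withdrawal visit. This concerns a secondary endpoint and does not touch the NNAL analysis. It is worth correcting because the correction is cheap.

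**What to change.** No clinical rule needs to change.

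1. In 3.3.2, state that the week-16 questionnaires will be sought from all randomised participants whatever the reason for withdrawal, remotely if needed and subject to consent, and that these scores enter the intention-to-treat analysis. Section 7.2 already provides for phone data collection and emailed or texted questionnaires.
2. In 8.3, add a comparison of the proportion with a suicide attempt, psychiatric hospitalisation or psychiatric withdrawal, VLNC (arms 3 and 4) v NNC (arms 1 and 2), with a 95% CI, reported beside the Kessler-6 difference.
3. Add a worst-rank or other missing-not-at-random analysis of Kessler-6 as a sensitivity analysis only. Worst-rank is a debatable choice of estimand, and in the 80%-withdrawn illustration it reaches only about 22% power, so it should not be the main method. State that absence of mental-health harm will not be concluded from the ANCOVA alone.

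The cost is a little extra follow-up contact and one extra table; withdrawal reasons and adverse events are already recorded. The event comparison has limited power (about 54% for 8% v 1.6%, 28% for 5% v 1%), so its interval should be read as the range of harm not excluded, not as a pass or fail test.

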(VOCs). The health effects of heated and aerosolized constituents of e-cig liquids, including solvents, flavors, and toxicants, are not completely understood.(19) However, some studies suggest e-cigs, when used exclusively, have a more favorable toxicity profile than tobacco cigarettes.(20, 21) E-cigs have become increasingly popular among cigarette smokers, particularly SMHC. For example, in the PATH Wave 1 survey, cigarettes plus e-cigs was by far the most common pattern of combined use.(2) In a large population survey from 2015, people with a mental health condition were twice as likely to be current cigarette smokers and twice as likely to be current e-cig users as people without a mental health condition.(14) This study aims to assess the likely health effects of a product standard lowering the nicotine content of cigarettes in SMHC when having access to e-cigs.

It is highly likely that in a scenario in which FDA issued a product standard requiring only very low nicotine content in cigarettes, existing smokers may attempt to supplement their nicotine from alternative sources. Given the current prevalence of e-cig use among current and former smokers, they are a prime candidate for such a source. To date, most studies designed to evaluate the likely effects of a low nicotine product standard for cigarettes have required participants to only use the specially designed reduced nicotine content cigarettes without supplementation from their own cigarettes or any other nicotine sources.(4, 8) This was a reasonable research design, however it has become clear that a significant proportion of those allocated to smoke only VLNC cigarettes were non-compliant, as their cotinine concentrations could not realistically be obtained from smoking only VLNC cigarettes.(22, 23) It seems most likely that the participants “topped off” their nicotine levels by occasionally smoking normal nicotine cigarettes. In the real world, if a product standard requiring only VLNC in cigarettes were to be implemented it is likely that alternate nicotine products, such as e-cigs, would also be available, so it is important to examine the patterns of product use and the resulting effects on biomarkers of toxicant exposure in that situation.

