2.2 Previous Data

Below, we summarize key relevant findings from our team’s recent research, which leads to both our interest and expertise in conducting this proposed study.

Research on Reduced Nicotine Content Cigarettes. In our recently completed trial, participants were randomly assigned to smoke either (a) NNC cigarettes (11.6 mg/cig); or b) Reduced Nicotine Content (RNC) cigarettes where the nicotine content per cigarette is progressively reduced to 0.2 mg/cig in five steps over 18 weeks. Participants were then offered the choice to either (a) quit smoking with assistance, (b) continue smoking the research cigarettes, or (c) return to their own cigarettes, and were followed up for a further 12 weeks. After controlling for the baseline measure, plasma cotinine, exhaled CO and FTND score were all significantly lower at the end of randomized phase in the RNC group as

compared to the NNC group. Measures of nicotine dependence (mean cigarettes smoked per day, Penn State Cigarette Dependence Index) were significantly lower at the end of the randomized phase in the RNC group, as compared to the NNC group ($p<0.003$), whereas measures of psychiatric problems (CES-D depression score, QIDS depression score, OASIS anxiety score and MNWS nicotine withdrawal score) showed no significant change in the RNC group as compared to the NNC group. Analyses focusing on those participants who were compliant with exclusive use of research cigarettes throughout the randomized phase of the trial (in the RNC group having a reduction in mean cotinine from 245 ng/ml at visit 4 to 8 ng/ml at visit 10), found an almost identical pattern of results to the randomized phase completer analysis.

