7.4.4 Subject Compliance Monitoring

Compliance will be monitored throughout the trial by a) daily product use logs; b) product accountability logs where the amount of product dispensed will be recorded and unused products collected and recorded; and c) questionnaires administered during study contacts regarding the use of other tobacco or nicotine products. Any problems that arise or are anticipated will be discussed and problem-solved with the coordinator. Furthermore, exhaled CO measurements will be collected throughout the study to verify smoking intensity and exposure levels.

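### The planned comparison of compliers and non-compliers within arm 4 is open to confounding by amount smoked, and can show lower NNAL in compliers when compliance has no effect

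*Combined protocol and SAP*

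**What the plan says.** Section 8.3 states: "For participants in arm 4 (VLNC plus placebo ecigs) their compliances will be further evaluated using biomarkers". The next sentence is the analysis at issue: "Comparison on the outcome variables will be made between compliers vs non-compliers within arm 4 participants only". The section gives no marker, cut-off, visit, model or covariates for it, and does not call it descriptive or exploratory. The same paragraph makes all tests two-sided at 0.05.

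Other sections suggest two candidate markers.

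- **Cotinine.** Section 2.1 says of participants in earlier VLNC trials that "their cotinine concentrations could not realistically be obtained from smoking only VLNC cigarettes". Section 2.2 describes compliant participants in the team's previous trial as "in the RNC group having a reduction in mean cotinine from 245 ng/ml at visit 4 to 8 ng/ml at visit 10". Section 1.3 lists cotinine as an endpoint without a visit, but the urine row of Table 1 names only NNAL, CYMA and 3-HPMA.
- **Exhaled CO.** Section 7.4.4, on compliance, says "exhaled CO measurements will be collected throughout the study to verify smoking intensity and exposure levels". CO is also a secondary endpoint (1.3).

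For the main between-arm analyses, 8.3 says "Intent-to-treat (ITT) principle will be adopted for the analyses in both approaches", and describes ANCOVA models comparing final values "while the baseline measurements will be treated as controlled covariates in the model". The closing sentence on adjusted models concerns the treatment effect. Neither provision is extended to the arm 4 contrast.

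**The concern.** The two groups are defined by something that happens after randomisation, and both lie in one arm, so randomisation protects nothing in the comparison. The classifier is not independent of the outcome either. Nicotine exposure is cigarettes smoked times nicotine per cigarette, and NNAL and CO also rise with cigarettes smoked. CO as the marker would split the arm directly on smoking intensity and would be one of the outcomes being compared.

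Abstainers add a second route. Someone who has stopped smoking has low nicotine and low NNAL, so a simple low-nicotine rule counts them as compliers. The trial expects some: Aim 3 tests whether VLNC cigarettes increase complete switching away from combustible tobacco by week 16.

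At stake is a tested contrast that a reader could take as the benefit of using VLNC cigarettes exclusively. Section 2.1 treats non-compliance as the known weakness of this literature, and 2.3 says the trial should inform a regulatory decision.

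**Working it through.** **Yardstick from the plan.** The documents give no figure for the complier comparison. Section 8.2 cites a NNAL ratio of 0.78 from an earlier trial, and ln 0.78 = −0.248 reproduces. With its SD of 0.562 and effect of 0.58 SD, the planning difference is 0.58 × 0.562 = 0.326, a ratio of exp(−0.326) = 0.72.

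**How smoking amount enters.** Take the plan's 0.2 and 11.6 mg per cigarette, and assume 15 cigarettes/day. A typical normal-nicotine level is 15 × 11.6 = 174 mg, so a 10% cut-off is 17.4 mg. A participant for whom 10% of cigarettes are normal takes in 0.1 × 11.6 + 0.9 × 0.2 = 1.34 mg per cigarette:

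| Cigarettes/day | Nicotine (mg) | Class at 17.4 mg |
|---|---|---|
| 7.5 | 10.05 | complier |
| 15 | 20.1 | non-complier |
| 30 | 40.2 | non-complier |

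The normal-cigarette share is the same in each row, and only the amount smoked changes the class.

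**General size.** Suppose the marker correlates ρ with log NNAL and has no causal effect, and a fraction p are called compliers. With c = Φ⁻¹(p), the difference (complier minus non-complier) is −ρ × SD × φ(c) / [p(1−p)].

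- ρ = 0.3, p = 0.5: −0.3 × 0.562 × 0.3989/0.25 = −0.269, ratio 0.76.
- ρ = 0.3, p = 0.25 or 0.75: −0.3 × 0.562 × 0.3178/0.1875 = −0.286, ratio 0.75.
- ρ = 0.1 gives a ratio of 0.91; ρ = 0.2 gives 0.83–0.84.

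With 60 participants, a t-test at 0.05 rejects falsely in 8–9% of trials at ρ = 0.1, 18–23% at 0.2 and 38–47% at 0.3. At ρ = 0 it holds its level. The values of ρ and p are assumptions.

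**Simulation with a null compliance effect.** All inputs except the nicotine contents are assumptions: consumption lognormal around 15/day, log-SD 0.5; half the arm uses normal cigarettes, with a Beta(1,4) share (mean 20%) unrelated to consumption; nicotine measured with log-SD 0.4; NNAL proportional to total cigarettes with log-SD 0.5; fixed cut-off at 5–20% of the typical normal-nicotine level. Baseline and week-16 smoking are taken to correlate at about 0.7 for the adjusted column.

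| Abstainers (counted as compliers) | Raw ratio | Baseline-adjusted ratio |
|---|---|---|
| none | 0.76–0.84 | 0.83–0.89 |
| 5–10%, residual NNAL 2–20% of typical | 0.44–0.75 | 0.46–0.79 |

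The adjusted figures move by about 0.02 with how baseline noise is modelled. Grouping by true compliance gives 0.99–1.00. A per-cigarette cut-off with no abstainers gives 1.00. Removing abstainers from the complier group and adjusting for baseline returns the ratio to 0.83–0.89.

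The abstainer result depends on residual NNAL because the outcome is on the log scale. Abstainers forming 10% of a complier group that is otherwise at the typical level multiply its geometric mean by exp(0.1 × ln 0.02) = 0.68, or by exp(0.1 × ln 0.20) = 0.85.

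**Sensitivity to the pattern of non-study use.** A second null model (mean 16 cigarettes/day, n = 60, no abstainers, fixed cotinine cut-offs of 8, 20 and 50 ng/ml) gives:

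| Non-study cigarettes | Fixed cut-off, raw | Fixed, baseline-adjusted | Per-cigarette cut-off, raw |
|---|---|---|---|
| More likely in heavier smokers | 0.66–0.70 | 0.89–0.92 | 0.74–0.77 |
| Random share of consumption | 0.79–0.88 | 0.91–0.95 | 1.00 |
| Random count | 0.86–0.97 | 0.94–0.99 | 1.02–1.12 |

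**The case against.** The strongest reply is that cotinine would separate mainly on non-study nicotine, not on amount smoked. The cigarettes differ 58-fold in nicotine (11.6/0.2), and compliant participants in the earlier trial fell from 245 to 8 ng/ml. An exclusive VLNC smoker would need 17.4/0.2 = 87 cigarettes a day to fail the 10% cut-off above. This stands in part: with cotinine, sorting by amount smoked acts among those who mix products and through abstainers.

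The plan also has daily use logs, so a consumption-based rule is possible, and its main models use baseline covariates. Both help. The first removes the bias only if there are no abstainers and non-study use is unrelated to smoking level. The second removes only part of it when abstainers are present, because quitting happens after baseline. Neither is written into the arm 4 contrast.

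Restricting biomarker compliance to arm 4 is sensible, since no other arm is without a nicotine-containing e-cig or a normal-nicotine cigarette. No aim or endpoint rests on the contrast, and the plan makes no causal claim for it.

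A reader might infer that the contrast must favour compliers, or that the plan gives up its randomised comparison. The documents support neither. The marker and rule are unstated and some rules give a null or reversed ratio, while the randomised comparison of arms 2 and 4 remains in 8.3.

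**Conclusion.** The concern holds as a likely bias, not a certain one, in a stated secondary analysis. As written, the within-arm 4 contrast can produce a spurious NNAL ratio of about 0.76–0.84 with a fixed cut-off and no abstainers, and about 0.44–0.75 with 5–10% abstainers counted as compliers. That is comparable with, or larger than, the 0.78 cited in 8.2. These sizes rest on the assumed smoking distribution, pattern of non-study use and cut-off, and the abstainer range also on residual NNAL of 2–20% of typical. The bias vanishes with a per-cigarette cut-off, no abstainers and non-study use unrelated to smoking level. The primary intention-to-treat analysis of NNAL is not affected.

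**What to change.** In 8.3:

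1. Report arm 4 participants with no cigarette use as their own category, not as compliers.
2. Make the compliance analysis a comparison of arm 4 compliers with arm 2 (normal-nicotine cigarettes plus placebo e-cig), adjusted for Visit 3 NNAL and for baseline cigarettes per day and dependence. Name the marker, cut-off and visit in advance. Inverse-probability-of-compliance weighting can be an optional sensitivity analysis; in a 60-person arm the weights may be unstable.
3. If the within-arm 4 table is kept, adjust it for the same baseline values and present it descriptively, without a test and not as an effect of compliance.

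The cost is SAP wording and one extra model on NNAL, consumption and dependence data already planned; if cotinine is the marker, its collection visits also need stating. Intervals will be wider. The comparison with arm 2 still sets a selected subgroup against a whole arm, so it relies on the measured baseline factors to explain compliance.
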